Study Duration: Subjects will be followed for 24 weeks after the last study product administration.

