Assessment of potential “off target” binding in a GLP tissue cross-reactivity study with normal adult human and rat (Sprague Dawley) tissues	
VRC07-523LS staining that was observed in both human and Sprague-Dawley rat tissues included cytoplasm, cytoplasmic granules, perinuclear, and/or apical cytoplasm of endothelium, epithelial cells, spindle cells, mononuclear cells, granulosa lutein cells, and neural cell processes.
 
VRC07-523LS staining that was observed in human tissues only included cytoplasmic elements of hematopoietic cells, cells/processes associated with peripheral nerve, glial cell processes, reticular cells, mesothelial cells, interstitial cells, and adipocytes, and extracellular proteinaceous material in connective tissue of the sclera. VRC07-523LS staining that was observed in rat tissues only included the cytoplasm of rare decidua cells and lens protein. According to ICH S6(R1) and other references [17, 18], monoclonal antibody binding to cytoplasmic sites generally is considered of little to no toxicologic significance. The specific staining of extracellular proteinaceous material in eye (human tissue) and staining for lens protein in eye (rat tissue) further support the rat as a relevant species to assess safety.
 
Additionally, histologic changes were not observed in the GLP repeat dose toxicology study in the cell types with staining observed in the GLP TCR study.

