4. STUDY DESIGN

This is an open-label, dose-escalation study to examine the safety, tolerability, dose, and PK of VRC07-523LS in healthy adults. The hypothesis is that VRC07-523LS administration will be safe by the IV and SC routes. The secondary hypothesis is that VRC07-523LS will be detectable in human sera with a definable half-life. The study schema is shown in Table 3.

Table 3: VRC 605 Study Schema

Group	Subjects	Administration Schedule		
		Day 0	Week 12	Week 24
1	3	1 mg/kg IV		
2	3	5 mg/kg IV		
3	3	5 mg/kg SC		
4	3	20 mg/kg IV		
5	3	40 mg/kg IV		
6	5	5 mg/kg SC	5 mg/kg SC	5 mg/kg SC
7	5	20 mg/kg IV	20 mg/kg IV	20 mg/kg IV
Total*	25	*The expected enrollment is 25 subjects. Enrollment up to a total of 40 subjects is permitted if additional subjects are necessary for safety or PK evaluations (Section 4.3).		

Enrollment will begin in the 1 mg/kg IV dose group (Group 1). Enrollments into the subsequent dose and route groups may proceed after dose and route escalation reviews (Section 4.3). Subjects in Groups 1 through 5 will be expected to be available for follow-up visits during 24 weeks of study participation; subjects in Groups 6 and 7 will be expected to be available for follow-up visits during 48 weeks of study participation

For each new dose level (1 mg/kg, 5 mg/kg, 20 mg/kg and 40 mg/kg) and for the initial SC group, following the first product administration, the study team will wait at least 2 days before administering VRC07-523LS to a second subject within the same group. Safety review decisions and the status of the enrollment process will be transparent to the Protocol Safety Review Team (PSRT) throughout the trial and discussed during the weekly safety review.

Safety laboratory samples will be collected throughout the study as per the Schedule of Evaluations. Subjects will keep a daily diary of solicited systemic symptoms for 3 days after each product administration. PK samples will be collected at specified intervals through 24 weeks after a subject's last product administration.

When the subject agrees, optional oral samples will be collected at specified intervals for the purpose of detecting if measurable levels of VRC07-523LS can be found in oral mucosa.

The study will be conducted by the VRC Clinical Trials Program at the NIH Clinical Center (NIH CC).

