Clinical laboratory assays and clinical evaluations will assess safety and tolerability at specified intervals after each administration. Throughout the study, clinicians will also assess subjects for any changes in symptoms to include vision changes. Any new or concerning symptoms will be fully assessed to include specialty consultation at the NIH Clinical Center as indicated clinically.

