5. SAFETY AND ADVERSE EVENT REPORTING

5.1 ADVERSE EVENTS

An adverse event (AE) is any untoward or unfavorable medical occurrence in a human subject, including any abnormal sign (e.g., abnormal physical exam or laboratory finding), symptom, or disease temporally associated with the use of study treatment, whether or not considered related to the study treatment.

Severity of AEs will be assessed using the Version 2.0 of the *DAIDS Table for Grading the Severity of Adult and Pediatric Adverse Events* [November 2014]. The table is available at: http://rsc.tech-res.com/Document/safetyandpharmacovigilance/DAIDS_AE_GRADING_TABLE_v2_NOV2014.pdf. Additional information can be found in Appendix IV.

Reporting of all AEs will occur during the period from first study product administration through 56 days after each study product administration. After this through completion of study participation only serious adverse events (SAEs) and new chronic medical conditions that require ongoing medical management will be recorded as AEs in the study database.

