6.4.3 Safety Analysis

Summaries of the number and percentage of subjects experiencing any AE or reactogenicity will be tallied by subgroup, and presented along with exact 95% confidence intervals for the proportion.

Solicited AEs: Solicited AE data is collected after each dose administered in this study. The number and percentage of subjects experiencing each type of solicited sign or symptom will be tabulated by severity. For a given sign or symptom, each subject's solicited AEs will be counted once under the maximum severity for all assessments.

Unsolicited AEs: Unsolicited AEs are coded into MedDRA preferred terms. The number and percentages of participants experiencing each specific AE will be tabulated by severity and relationship to treatment. For the calculations in these tables, each participant's adverse experience will be counted once under the maximum severity or strongest recorded causal relationship to treatment.

A complete listing of adverse experiences for each participant will provide details including severity, relationship to treatment type, onset, duration and outcome.

Local Laboratory Values: Boxplots of local laboratory values will be generated for baseline values and for values measured during the course of the study. Each boxplot will show the 1st quartile, the median, and the 3rd quartile. Outliers, or values outside the boxplot, will also be plotted. If appropriate, horizontal lines representing boundaries for abnormal values will be plotted.

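### Vision changes are asked about throughout the study, but a transient, non-serious one starting more than 56 days after a dose is not recorded as an AE and cannot appear in the safety tables or listing

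*Combined protocol and SAP*

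**What the plan says.** Section 4.2.4 sets a surveillance duty with no time limit: "Throughout the study, clinicians will also assess subjects for any changes in symptoms to include vision changes". Vision is the only symptom named in that sentence. It is not among the solicited systemic or local parameters in the same section, so a vision complaint can enter the AE data only as an unsolicited event.

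Section 5.1 sets the recording rule: "Reporting of all AEs will occur during the period from first study product administration through 56 days after each study product administration". For the rest of participation, "only serious adverse events (SAEs) and new chronic medical conditions that require ongoing medical management will be recorded as AEs in the study database".

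Follow-up runs well past that window. The Précis states: "Subjects will be followed for 24 weeks after the last study product administration". Section 4 adds that "subjects in Groups 6 and 7 will be expected to be available for follow-up visits during 48 weeks of study participation". Appendix III schedules clinic visits with an interim medical history through the end of follow-up.

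On analysis, Section 6.4.3 says: "Unsolicited AEs are coded into MedDRA preferred terms". These events are tabulated by severity and relationship, and a per-participant listing includes onset and duration. Section 8.3.2 says that both the safety review team and the statistician work from data extracted from the clinical database.

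**The concern.** Sections 4.2.4 and 5.1 do not fit together. One asks clinicians to look for a named symptom up to the last visit. The other closes the AE database to most forms of that symptom 56 days after a dose. A subject who reports a week of blurred vision at the Week 16 visit of a single-dose group has been asked as intended, but under Section 5.1 the answer is not recorded as an AE unless the episode is judged serious or becomes a chronic condition.

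Safety and tolerability are the primary objectives of this first-in-human study. If the final tables show no late vision events, a reader cannot tell whether none occurred or none were eligible for recording. The safety review team, which continues monthly review to the last visit (Section 7.12), faces the same limit in the extracted AE data.

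**Working it through.** **Inputs.** Doses are on Day 0 (Groups 1-5) and on Days 0, 84 and 168 (Groups 6-7), from Table 3. The all-AE window is 56 days after a dose (Section 5.1). Follow-up ends on Day 168 or Day 336 (Précis, Section 4, Appendix III). Group sizes are 3 and 5 (Table 3).

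**1. The plan's own sensitivity figures (Section 6.3.2).** The true rate that gives a 90% chance of at least one event is 1 − 0.1^(1/n).
- n = 3: 0.5358 (plan: 0.536)
- n = 5: 0.3690 (plan: 0.37)

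Both reproduce. Section 6.3.2 introduces them for serious events, which Section 5.1 records to the end of the study, so the plan's figures are not in error.

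**2. Days on which a transient, non-serious event is not recorded as an AE.**
- Groups 1-5: Days 57-168, 168 − 56 = 112 days; 112/168 = 67%.
- Groups 6-7, window unbroken to 56 days after the third dose (Day 168 + 56 = Day 224): Days 225-336, 112 days; 112/336 = 33%.
- Groups 6-7, window restarting at each dose: Days 57-83 (27 days), Days 141-167 (27 days) and Days 225-336 (112 days). The sum is 27 + 27 + 112 = 166 days; 166/336 = 49%.

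Section 5.1 does not say which reading applies to repeat dosing.

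**3. Visits affected.** In every group the last four scheduled visits fall outside the window: Days 84, 112, 140 and 168 in Groups 1-5, and Days 252, 280, 308 and 336 in Groups 6-7.

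**4. Illustration for a non-serious event class.** For an event that both starts and resolves outside the window, the chance of appearing in the AE data under the Section 5.1 rule is 0 at any true rate. If onset is assumed to be uniform over follow-up, a true rate p is recorded at p × (covered share), and the chance of at least one recorded event is 1 − (1 − p × share)^n.
- n = 3, p = 0.536, share 56/168: 1 − (1 − 0.179)^3 = 0.45
- n = 5, p = 0.37, share 170/336 (restarting): 1 − (1 − 0.187)^5 = 0.65
- n = 5, p = 0.37, share 224/336 (unbroken): 1 − (1 − 0.247)^5 = 0.76

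With full recording each of these would be 0.90. The uniform-onset assumption is mine; the documents give no onset pattern.

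**The case against.** Several stronger readings are tempting, and the documents do not support them.

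- A reader might infer that a late vision change would go unreported altogether. Section 5.1 limits only what is recorded as an AE in the database. Section 4.2.4 goes on to require full assessment of new or concerning symptoms, with specialist referral where indicated. An event could be judged serious as an important medical event (Section 5.2), be reported as an SAE on the investigator's judgement (Section 5.3), qualify as an unanticipated problem (Section 5.4.1), or be reported at continuing review as a trend or notable event (Section 5.4.5). Nor do the documents say whether interim history enters the database in some other form. All this stands, but these routes depend on judgement and none is stated to feed the Section 6.4.3 outputs.
- A reader might blame the lack of an ocular grouping in Section 6.4.3. It loses no late event; the loss comes from Section 5.1 alone. Among at most 40 subjects, recorded eye terms can be picked out of the listing, which gives onset.
- A reader might treat the eye staining in Table 1 (Section 2.3) as the reason for the vision question, or as a sign of ocular hazard. Section 4.2.4 gives no reason. Table 1 uses the staining to support the rat as a relevant species and adds that the toxicology study found no histologic changes in the stained cell types. No ocular effect is reported in animals or humans.
- A reader might size the problem by late drug exposure. The documents give no human half-life for this product. On an assumed mono-exponential decline, 2^(−56/t) gives 8% of terminal-phase exposure after Day 56 at t = 15.4 days (the VRC01 value in Section 1.1) and 28% at twice that. The point does not rest on these shares.

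It is also fair to say that Section 5.1 treats every late transient symptom alike. Vision differs because Section 4.2.4 singles it out by name for the whole study.

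**Conclusion.** The concern holds as a mismatch between elicitation and recording. A transient, non-serious vision change starting more than 56 days after a dose is asked about but not recorded as an AE, so it is absent from the AE tables and listing that serve the primary objective. The uncovered share is 67% of follow-up in Groups 1-5 and 33% or 49% in Groups 6-7, depending on how the window is read. Those shares follow from the stated schedule and need no assumption beyond that reading. The fall from 90% to 45%, 65% or 76% is only an illustration under uniform onset.

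The conclusion does not extend to serious events, to new chronic conditions under continuing management, or to vision symptoms that start within 56 days of a dose. All of these are recorded. It makes no claim that the product affects the eye.

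**What to change.** Reconcile Section 4.2.4 with Section 5.1. Add new or changed vision symptoms to the events recorded as AEs in the database through the last study visit, whatever their seriousness or duration. They then enter the existing Section 6.4.3 tables and listing with no change to the analysis. In the same edit, state whether the 56-day window in Groups 6-7 runs unbroken to 56 days after the last dose or restarts at each dose.

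This changes data recording only. Clinicians already ask the question, so the cost is a few extra database entries. The drawback is that some recorded symptoms will be background events unrelated to product, with no control group to set them against. With this change, vision symptoms are covered on 168 of 168 days in Groups 1-5 and 336 of 336 in Groups 6-7. A combined row in Section 6.4.3 for any vision symptom is optional and not needed to close the gap.

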4.2.5 Pharmacokinetics

PK samples will be collected as close as reasonably possible to the target timepoints. However, actual time of collection is critical for PK analysis and will be recorded for all samples. The PK timepoints are shown in the Schedule of Evaluations.

4.2.6 Oral Mucosa Samples

To understand tissue distribution of VRC07-523LS and how long after administration it may be detectable, this protocol includes exploratory collection of oral mucosa samples. Subjects will be offered the option of participating in the oral sampling schedule, but it will not be mandatory. Samples will be collected using small ophthalmic sponges designed for clinical use.

Oral swabs for research may be collected per the Schedule of Evaluations, Appendix III.

4.2.7 Schedule of Evaluations

The Schedule of Evaluations, Appendix III, provides details on the study schedule and the permitted visit windows. Schedule 1 is for the IV dose escalation groups receiving one injection (Groups 1, 2, 4, and 5), Schedule 2 is for the SC dose group receiving one injection (Group 3). Schedule 3 and Schedule 4 are for the groups receiving repeat dosing; Group 6 (5 mg/kg SC) and Group 7 (20 mg/kg IV). The schedules also include instructions for evaluations of subjects who discontinue

product administration. After enrollment, deviations from the visit windows are discouraged but will be permitted at the discretion of the PI or designee and will be recorded as protocol deviations.

Additional visits and blood draws may be scheduled during the study if needed to assess subject safety or for sample collection for immunological testing. After study completion, subjects may be invited to participate in one of the VRC sample collection protocols (VRC 200 or VRC 900) for follow-up sample collection.

Any evaluation for an AE or possible exacerbation of a pre-existing condition may be evaluated at study team discretion as a “protocol related” evaluation.

4.2.8 Concomitant Medications

Only routine prescription medications will be entered in the database at the time of enrollment. Subsequently, concomitant medications associated with an AE that requires expedited reporting or the development of a new chronic condition requiring ongoing medical management will be recorded in the database. Receipt of a FDA-approved vaccine at any time during the study will be recorded in the database (clinicians should work with subjects regarding the timing of licensed vaccines relative to study product administration). Otherwise, concomitant medications taken throughout the study will be recorded in the subject’s chart as needed for general medical documentation but will not be recorded in the database.

4.3 CRITERIA FOR DOSE AND ROUTE ESCALATION

There are three dose escalation reviews in this study and one route escalation review. The Protocol Safety Review Team (PSRT, Section 8.9) will conduct an interim safety data review before dose escalation and repeat dosing may occur. The PSRT must assess the data as showing no significant safety concerns before proceeding with enrollment of the next groups.

- The first dose escalation review (from 1 mg/kg IV to 5 mg/kg IV) will occur when at least 3 subjects who received the 1 mg/kg IV dose have completed 2 weeks of safety follow-up visits. The PSRT review will determine if enrollments in Group 2 may begin.
- The only route escalation review and the second dose escalation review (from 5 mg/kg IV to 5 mg/kg SC and 20 mg/kg IV, respectively) will occur when at least 3 subjects who received the 5 mg/kg IV dose have completed 2 weeks of safety follow-up visits. The PSRT review will determine if enrollments in Group 3 (5 mg/kg SC), Group 6 (5 mg/kg SC by repeat dosing), Group 4 (20 mg/kg IV) and Group 7 (20 mg/kg IV by repeat dosing) may begin.
- The third dose escalation review (from 20 mg/kg IV to 40 mg/kg IV) will occur when at least 3 subjects who received the 20 mg/kg IV dose have completed 2 weeks of safety follow-up visits. This review will determine if enrollments in Group 5 (40 mg/kg IV) may begin.
- Additionally, the second and third doses can be administered in Groups 6 and 7 once the initial dose is assessed as safe for further evaluation.

If the first product administration is not completed or there are discontinuations from the study before there are sufficient data to conduct the dose escalation review for a group, then extra subjects may be enrolled into that group in order to have the requisite data on at least 3 subjects.

Additionally, AEs assessed as related to the study product at the time of a dose escalation review may be judged by the PSRT to warrant adding additional subjects at a given dose group.

The IRB will be provided with documentation of the safety review process and notification of the dose escalation. Consultation with the IRB and FDA, if needed, as per study pause criteria (Section 4.5) will occur if indicated by the review. One outcome of a dose escalation review may be to recommend evaluation of additional subjects at the current dose and reassess for safety before proceeding to a higher dose.

4.4 CRITERIA FOR DISCONTINUATION OF VRC07-523LS ADMINISTRATION

Under certain circumstances, a subject may be terminated from participating in study product administrations. Subjects who receive at least one VRC07-523LS administration will continue follow-up according to the protocol Schedule of Evaluations, except that the research sample collections will be discontinued for pregnant women or others in which it is contraindicated. The study team will notify the antiretroviral pregnancy registry (<http://www.apregistry.com>) of any pregnancies that occur after receiving VRC07-523LS for any subject still on study. Specific events that will require discontinuing a subject from receiving the study product include:

1. Pregnancy;
2. Grade 3 AE assessed as related to the study product (with the exception that self-limited Grade 3 solicited reactogenicity does not require discontinuation of product administration);
3. Grade 4 AE assessed as related to the study product;
4. Immediate hypersensitivity reaction associated with the study product;
5. Intercurrent illness that is not expected to resolve prior to the next scheduled study product administration which is assessed by the PI (or designee) to require withdrawal from the product administration;
6. Repeated failure to comply with protocol requirements;
7. Co-enrollment into a study in which other investigational research agents will be administered before the subject has completed the follow-up after the last VRC07-523LS administration;
8. The IND sponsor or the study PI decide to stop or cancel the study;
9. The IRB, Office for Human Research Protections (OHRP) or the FDA halt the study.

4.5 CRITERIA FOR PAUSING THE STUDY AND RESUMING THE STUDY

Administration of the study product and new enrollments will be paused by the PI according to the criteria noted below. In the event of a pause, the IND Sponsor Medical Officer (MO) and the PSRT will be promptly notified. Pause criteria are as follows:

One (or more) subject experiences a **Serious Adverse Event** (SAE) that is assessed as related to study product, or

Two (or more) subjects experience the same **Grade 3 or higher AEs** assessed as related to study product (other than self-limited Grade 3 solicited reactogenicity AEs).

Plan for Review of Pauses and Resuming Rules:

Study product administration and enrollments would resume only if review of the AEs that caused the pause results in a recommendation to permit further study product administrations and study enrollments. The reviews to make this decision will occur as follows:

Pauses for related SAEs: The IND Sponsor, with participation by the PI, will consult with the FDA to conduct the review and make the decision to resume, amend or close the study and will notify the IRB accordingly.

Pauses for Grade 3 or higher related AEs: The IND Sponsor MO, in consultation with the PI, will conduct the review and make the decision to resume, amend or close the study for the Grade 3 or higher AEs that meet criteria for pausing the study. As part of the pause review, the reviewers will also advise on whether the study needs to be paused again for any subsequent events of the same type. The FDA and the IRB will be notified of Grade 3 or higher pause reviews and of the IND Sponsor's decisions.

5. SAFETY AND ADVERSE EVENT REPORTING

5.1 ADVERSE EVENTS

An adverse event (AE) is any untoward or unfavorable medical occurrence in a human subject, including any abnormal sign (e.g., abnormal physical exam or laboratory finding), symptom, or disease temporally associated with the use of study treatment, whether or not considered related to the study treatment.

Severity of AEs will be assessed using the Version 2.0 of the *DAIDS Table for Grading the Severity of Adult and Pediatric Adverse Events* [November 2014]. The table is available at: http://rsc.tech-res.com/Document/safetyandpharmacovigilance/DAIDS_AE_GRADING_TABLE_v2_NOV2014.pdf. Additional information can be found in Appendix IV.

Reporting of all AEs will occur during the period from first study product administration through 56 days after each study product administration. After this through completion of study participation only serious adverse events (SAEs) and new chronic medical conditions that require ongoing medical management will be recorded as AEs in the study database.

